### **13.6 Record Retention**

The investigator will retain study records including source data, copies of case report form, consent forms, HIPAA authorizations, and all study correspondence in a secured facility for at least 6 years after the study file is closed with the IRB.

Please contact the CTO before destroying any study related records.

## **14 Study Endpoints**

### **14.1 Primary Endpoint**

Efficacy is measured by overall survival (OS) at 6 months.

### **14.2 Secondary Endpoints**

Secondary endpoints of safety and efficacy are measured as below.

- OS at 12 months
- Cumulative incidence of grade II-IV acute graft-versus-host disease (aGVHD II-IV) at 3 months
- PFS at 6 and 12 months in patients
- Cumulative incidence of relapse at 6 and 12 months
- Complete remission (CR) at 6 and 12 months
- Cumulative incidence of non-relapse mortality (NRM) at 6 and 12 months
- Best response until next line of treatment, death, or last follow up, whichever occurs sooner

### **14.3 Correlative Endpoints**

- Incidence and severity of adverse events (AEs) and serious AEs (SAEs) until 3 months after day 1 of the last received cycle
- Correlative studies: T cell and NK cell subset analysis by flow cytometry, correlation between TP53 mutation and response, clonal dynamics during and after the course of therapy

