## Synopsis

Study Design:	
This is a multi-center, single-arm, open-label, phase II trial for the frontline treatment of relapsed AML or MDS following allo-HCT.
 
Eligible subjects will receive up to 4 cycles of combined modality treatment. The number of cycles depends on response, toxicity, and the remaining cell dose.
 
Cycles include:
 

• 10 days of decitabine 20 mg/m^2 IV daily, or, alternatively on a 5-2-5 schedule with no weekend infusion. If a CR is achieved after 2 cycles using the 10-day schedule, subsequent cycles will change to a 5-day schedule.

• Starting with day 1 of cycle 1 and continuing for up to 6 months after the end of the last cycle, patients will receive ruxolitinib 5 mg twice daily orally. Dose may be increased to 10 mg twice daily in cycles 2 through 4 if platelets improve to >100 x 10^9/L.

• DLI from the original donor will be infused within 10 days after the last dose of decitabine in each cycle.

 
Patients will be screened for ongoing eligibility before each subsequent cycle of therapy. Patients with disease progression, new GVHD (except grade I acute GVHD), prolongation of the most recent cycle to more than 8 weeks (for any reason), or inadequate cell dose for further DLI will not receive further treatment on study. The DLI dose in each cycle will be determined according to a donor-dependent dose-escalation algorithm (schema).
 
The expected duration of treatment for each subject is 4 cycles of treatment, each lasting 4-8 weeks. Subjects will be followed on study for 12 months.

Primary Objectives:	Determine the efficacy of combined modality treatment (ruxolitinib, 10-day decitabine, and DLI) for relapsed AML or MDS post allo-HCT.
Secondary Objectives:	

• Evaluate OS

• Determine incidence of grade II-IV acute graft-versus-host disease (aGVHD II-IV)

• Evaluate PFS

• Determine incidence of relapse

• Evaluate complete remission (CR)

• Determine incidence of non-relapse mortality (NRM)

• Best response

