### 1.3 Correlative Objectives

- To evaluate incidence and severity of adverse events (AEs) and serious AEs (SAEs) until 3 months after day 1 of the last received cycle
- Correlative studies: T cell and NK cell subset analysis by flow cytometry, correlation between *TP53* mutation and response, clonal dynamics during and after the course of therapy

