## 3 Study Rationale

In the proposed study, we add two novelties to the HMA-DLI platform with the goals of increasing efficacy and decreasing toxicity. First, while azacitidine is the more commonly used HMA in combination with DLI, we will replace azacitidine with 10-day courses of decitabine. This concept is based on two observations: (i) Unprecedented high response rates (100% in the recent report by Washington University investigators) to 10-day decitabine, particularly in *TP53*-mutated MDS/AML, and (ii) In a recent murine study, decitabine, but not azacitidine, potentiated the antileukemic activity of hematopoietic stem and progenitor cell-derived NK cells. Furthermore, the number of NK cells in the bone marrow was increased after decitabine treatment. The second novelty in this protocol is adding JAK2 inhibitor ruxolitinib to the HMA/DLI combination. JAK inhibition has shown clinical activity in the treatment of acute GVHD. Preliminary studies conducted by [name] have shown

that JAK inhibition decreases PDL1 expression of neoplastic cells and augment GVL while preventing GVHD ([Figure 1](#)).

**Figure 1:** Effects of JAK inhibition on PD-L1 expression on a murine B-cell lymphoma cell line

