#### 4 Study Design

This is a multi-center, single-arm, open-label, phase II trial for the frontline treatment of relapsed AML or MDS following allo-HCT.

Eligible subjects will receive up to 4 cycles of combined modality treatment. The number of cycles depends on response, toxicity, and the remaining cell dose.

Cycles include:

- 10 days of decitabine 20 mg/m^2 IV daily; or, alternatively, per institution, physician, or patient preference on a 5-2-5 schedule with no weekend infusion. If a CR is achieved after 2 cycles using the 10-day schedule, subsequent cycles will change to a 5-day schedule.
- Starting with decitabine and continuing for up to 6 months after the end of the last cycle, patients will receive ruxolitinib 5 mg twice daily orally.
- DLI from the original donor will be infused within 10 days after the last dose of decitabine in each cycle.

Patients will be screened for ongoing eligibility before each subsequent cycle of therapy. Patients with disease progression, new GVHD (except grade I acute GVHD), prolongation of the most recent cycle to more than 8 weeks (for any reason), or inadequate cell dose for further DLI will not receive further treatment on study. The DLI dose in each cycle will be

determined according to a donor-dependent dose-escalation algorithm (schema). If the collected cell dose in the DLI is less than the target dose, the patient will receive those collected cells and subsequently removed from further treatment cycles. These subjects will continue to be followed per protocol.

The expected duration of treatment for each subject is 4 cycles of treatment, each lasting 4-8 weeks.

Approximately 34 subjects will be enrolled (32 evaluable) over a period of 24 months, with an additional 12 months of follow up.

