## **8.8 Duration of Study Treatment**

The expected duration of treatment for each subject is 4 cycles of treatment, each cycle lasting 4 weeks; with up to 4 weeks of rescreening for eligibility to continue on to subsequent cycles; followed by six additional months of ruxolitinib. The following may be reasons for removal from additional study treatment:

- unacceptable toxicity
- disease progression

- new GVHD (except grade I acute GVHD)
- prolongation of the most recent cycle to more than 8 weeks (for any reason)
- inadequate cell dose for further DLI
- consent is withdrawn or patient is not compliant

Patients who are unable to receive further DLIs after initial cycle(s), may continue to receive ruxolitinib as long as the physician believes they are benefiting from the treatment, the patient has not withdrawn consent, and they have not developed unacceptable toxicity.

All patients receiving at least one cycle of treatment will be followed per [Sections 11.1](#) and [11.2](#) and be evaluable per [Section 15](#).

Patients unable to continue DLI may be treated per physician's choice. These patients will still be followed per [Sections 11.1](#) and [11.2](#).

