## 8.9 Duration of Study Participation

All patients must be followed for 12 months after the last dose of ruxolitinib for disease response and survival unless one of the following occurs earlier:

- consent is withdrawn
- new anti-cancer treatment is started (follow for survival only),
- patient is discharged to hospice (terminal) care (follow for survival only)

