## 11.1 Required Clinical Care Evaluations

	Screening within 28 days of study enrollment (within 14 days of C1D1 for eligibility labs)	Every Treatment Cycle		Between study cycles (day 29-56) 	Post DLI Visit (4-6 weeks after last DLI)	Follow-Up Q 3 months from the end of last cycle through 12 months
		During Decitabine admin	Day of DLI			
Written Consent	X					
Medical history	X					
Histological confirmation of diagnosis and staging	X					
Prior treatment	X					
Physical exam	X	X 	X		X	X
Provider assessment	X	X 	X			
Weight (Height also during screen)	X	X 				
Concomitant medications	X	X (day 1 each cycle)				
Karnofsky performance status	X			X		
ECG	X			X		
Type and Screen (ABO/RH/ Indirect Antiglobulin)	X					
Assessment of AEs	X	X	X		X	
Complete Blood Count with diff (CBC)	X	X 	X	X	X	X
Comprehensive Metabolic Profile (CMP) 	X	X 	X	X	X	X
HIV test	X					
Hepatitis B and C	X					
Pregnancy test (urine or serum) for WOCBP	X 			X		
Bone Marrow biopsy	X 			X 	X	
Relapse/progression status	X			X		
Survival status						X

MT2018-07: ruxolitinib, decitabine, and DLI for post-transplant relapse of AML or MDS

	Screening within 28 days of study enrollment (within 14 days of C1D1 for eligibility labs)	Every Treatment Cycle		Between study cycles (day 29-56) 	Post DLI Visit (4-6 weeks after last DLI)	Follow-Up Q 3 months from the end of last cycle through 12 months
		During Decitabine admin	Day of DLI			
Study treatment						
Decitabine		X (day 1-10 or day 1-5 & 8-12) 				
DLI			X (between 11-21 or 13-22) 			
Ruxolitinib		2 times a day				Through 6 months post end of last cycle
Research Nurse visit		Every two weeks			X	X

CMP to include sodium, potassium, chloride, creatinine, blood urea nitrogen, and liver function tests including AST, ALT, total bilirubin, and alkaline phosphatase

For women of childbearing potential (WOCBP): urine or serum pregnancy test within 14 days prior to study registration. If a urine test is positive or cannot be confirmed as negative, a serum pregnancy test will be required.

Continuous reassessment for eligibility to proceed to subsequent cycles

Results taken out of window may be used as enrollment verification and will not be considered a deviation.

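### The AE/SAE incidence endpoint closes about day 91 of the last received cycle, but ruxolitinib is planned to about day 211 and Section 12.2 monitors AEs to 30 days after the last dose

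*Combined protocol and SAP*

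**What the plan says.** **Endpoint.** Section 14.3 lists "Incidence and severity of adverse events (AEs) and serious AEs (SAEs) until 3 months after day 1 of the last received cycle". The Synopsis has the same window, and Section 1.3 states it as an objective: "To evaluate incidence and severity of adverse events (AEs) and serious AEs (SAEs) until 3 months after day 1 of the last received cycle". Section 15.2 summarises AEs by frequencies and proportions and names no window of its own.

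**Treatment.** The Synopsis starts ruxolitinib on day 1 of cycle 1, "continuing for up to 6 months after the end of the last cycle, patients will receive ruxolitinib 5 mg twice daily orally". Section 8.1, Tables 1 to 3 and the Section 11.1 calendar agree. For patients who can receive no further DLI, Section 8.8 adds that they "may continue to receive ruxolitinib as long as the physician believes they are benefiting from the treatment", subject to consent and toxicity. Section 12 defines study drug as ruxolitinib, decitabine and DLI together.

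**Capture.** Section 12.2 monitors AEs from consent to 30 days after the last dose of study drug. Most of its listed event types run to 30 days after the *last treatment on study*, a phrase it does not define. After the *final treatment visit*, also undefined, events at least possibly related to treatment are still documented when they become known. Under Sections 12.3 and 12.5, SAEs are reported to the last study visit or 30 days after the last dose, whichever is later.

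**Calendar.** In Section 11.1 the row "Assessment of AEs" is last marked at the post-DLI visit, 4 to 6 weeks after the last DLI. The 3-monthly follow-up column has no mark in that row, although the same column shows ruxolitinib continuing and includes a physical examination, blood counts, chemistry and a research nurse visit.

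**The concern.** The endpoint window is tied to the start of the last cycle, while ruxolitinib exposure is tied to its end plus six months. No text reconciles the two. A report that follows 14.3 literally would give AE and SAE incidence for the cycles and early maintenance only.

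This matters because ruxolitinib is one of the two features that set the regimen apart. Section 3 says: "The second novelty in this protocol is adding JAK2 inhibitor ruxolitinib to the HMA/DLI combination". Its expected toxicities in Section 9.1 include cytopenias, infection and sepsis, all of which can occur during maintenance. Section 9.3 also says that marrow aplasia after DLI may appear 1 to 6 months later, which reaches past the present cut-off.

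The calendar adds a second, practical problem. Section 12.2 expects AE monitoring through ruxolitinib plus 30 days, but sites working from 11.1 would see no scheduled AE assessment at the 3-monthly visits. Non-serious events in maintenance may then be collected unevenly between sites.

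**Working it through.** The plan states no figure for this point, so the check is calendar arithmetic counted from day 1 of the last received cycle.

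**Inputs**
- Endpoint window: 3 months from day 1 of the last received cycle (14.3), taken as 91 days.
- Ruxolitinib: up to 6 months after the end of that cycle (Synopsis, 4, 8.1), taken as 183 days.
- Final cycle length L: 28 days. Section 8.8 describes a 4-week cycle with up to 4 weeks of rescreening before a further cycle, so 28 days is the natural value for a final cycle. Section 4 gives 4 to 8 weeks, so 56 days is the upper bound.
- AE monitoring: last dose of study drug plus 30 days (12.2).

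**Windows**

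| Quantity | Formula | L = 28 | L = 56 (upper bound) |
|---|---|---|---|
| Endpoint closes | 91 | day 91 | day 91 |
| Planned ruxolitinib ends | L + 183 | day 211 | day 239 |
| 12.2 monitoring ends | L + 183 + 30 | day 241 | day 269 |
| Ruxolitinib days after endpoint closes | L + 183 − 91 | 120 | 148 |
| Share of the 183 maintenance days | (L + 92) / 183 | 65.6% | 80.9% |

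The month convention makes little difference. With months of 365.25/12 days and day 1 as the origin, the endpoint closes about day 92, and 118 days (65%) fall outside for L = 28.

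**As a share of all planned ruxolitinib.** For a patient who receives four 28-day cycles and completes maintenance, planned exposure is 4 × 28 + 183 = 295 days, of which 120/295 = 41% lies outside the endpoint.

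**Calendar.** The last DLI falls between day 6 (5-day schedule) and day 22 (5-2-5 schedule). The last marked AE assessment is 28 to 42 days later, from 6 + 28 = day 34 to 22 + 42 = day 64. With L = 28, the first 3-monthly visit is about 28 + 91 = day 119 and the second about 28 + 183 = day 211. Planned ruxolitinib runs through the first and ends about the second; neither carries an AE mark.

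**DLI risk period in 9.3.** Six months after a last DLI on day 6 to 22 is about day 189 to 205, also beyond day 91.

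**The case against.** The best defence is that an endpoint window and a capture window need not coincide. The 3-month window is stated consistently in three places and covers every decitabine and DLI day plus early maintenance. Nothing in 15.2 forbids tabulating later events. SAEs are reported for the longer period, grade III-IV aGVHD has its own window, and NRM is estimated to 12 months. This stands, and it is why the point is minor. It does not remove the mismatch: the endpoint as written stops at about day 91, no other AE incidence is planned, and the calendar does not schedule what 12.2 asks for.

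A reader might infer more in three ways, and the documents do not support these readings.

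- **Recording of non-serious listed events stops 30 days after the last DLI.** Section 4 uses the phrase loosely; patients with "inadequate cell dose for further DLI will not receive further treatment on study", although 8.8 lets them stay on ruxolitinib. Most of the text points the other way. The first sentences of 12.2 run to the last dose of study drug, and Section 12 includes ruxolitinib in that term. Section 7.2 begins study treatment with ruxolitinib and decitabine, 8.8 counts the six months of ruxolitinib in treatment duration, and 11.1 lists ruxolitinib under study treatment. Even on the narrow reading, possibly related events are still documented when known. The phrase needs defining, but recording does not simply close.
- **Late safety oversight is lost.** It is not; expedited SAE reporting covers maintenance.
- **A survival-adjusted share of person-time, or a count of patients alive at closure, can be quoted.** The endpoint closes at a date set by each patient's own last cycle, and the plan gives neither the distribution of cycles received nor how long patients stay on ruxolitinib.

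**Conclusion.** The mismatch is real and its effect is limited. For a patient who completes planned maintenance with a 4-week final cycle, about 120 of 183 maintenance days (66%) lie outside the reported AE/SAE incidence. The upper bound is 148 days (81%) and requires a 56-day final cycle. The 11.1 calendar conflicts with 12.2 over the same period.

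The figures assume that maintenance is completed. Six months is a maximum, the gap shrinks for patients who stop sooner, and it is nil for those who stop by day 91. They are shares of time; the plan gives no timing of AEs, so the share of events missed is unknown.

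The endpoint is descriptive and listed as correlative. The 6-month OS endpoint, the power and the aGVHD stopping rule do not depend on it. Severity is minor: a cheap improvement.

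**What to change.** - **Synopsis, 1.3 and 14.3:** extend the AE/SAE endpoint to the later of the present cut-off or 30 days after the last dose of any study drug, including ruxolitinib. For planned maintenance with a 4-week final cycle it then closes about day 241. Report the present window and the later maintenance period separately, so that the current summary is kept intact. Anchoring to the last dose also covers any patient whose ruxolitinib continues under 8.8.
- **12.2:** state that *last treatment on study* and *final treatment visit* include ruxolitinib.
- **11.1:** mark AE assessment at the existing 3-monthly visits while ruxolitinib continues.

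No new visits, tests or patients are needed. The cost is wording and modest extra data entry, more so if the sponsor had meant the phrase in 12.2 to refer to the last DLI. AE rates will look somewhat less favourable, and later events are harder to separate from relapse, which is a further reason to report the later period on its own.

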## **15 Statistical Considerations**

### **15.1 Objectives and Study Design**

This is a single-arm, open-label, multi-center modified Simon's two-stage phase II trial of a combined modality treatment for relapsed AML and MDS after allo-HCT. The primary endpoint is 6 month OS measured from day 1, cycle 1. We expect a total of 34 enrolled subjects will allow us to obtain 32 evaluable patients.

Patients are considered evaluable if they receive the first dose of decitabine and ruxolitinib. All other patients will be replaced.

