## **7.2 Patients Who Do Not Begin Study Treatment**

If a patient is registered to the study and is later found not able to begin study treatment (beginning with the ruxolitinib and decitabine); the patient will be removed from the study and treated at the physician's discretion. The study staff will update OnCore of the patient's non-treatment status (off study). The reason for removal from study prior to starting study treatment will be clearly indicated in OnCore. The patient will be replaced to complete enrollment.

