## 8.1 Chemotherapy Regimen

The administration of the preparative regimen will follow institutional drug and supportive care guidelines. Dose and/or schedule adjustments consistent with the standard of care may be made on an individual patient basis as needed for safety.

**Ruxolitinib** 5 mg twice daily orally beginning Day 1 and through Cycle 1. Consider dose increase to 10 mg twice daily in cycles 2 through 4 if platelets recover to over  $>100 \times 10^9/L$ . Ruxolitinib will continue through six months after the completion of the final cycle. See [section 8.4](#) for toxicity dose modification.

**Decitabine:** 20 mg/m^2 IV daily, on the following possible schedules: day 1-10 for cycles 1-2 (alternative: day 1-5 and day 8-12 with no weekend infusion); day 1-5 for cycles 3-4 (if CR achieved after Cycle 2). There are no dose modifications.

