**Table 5: Ruxolitinib dose adjustment**

CTCAE grade 3 or greater bleeding related to low platelets	Non-transfused platelets		
	<10 $\times 10^9$ /L	10-50 $\times 10^9$ /L	>50 $\times 10^9$ /L
Hold. Reassess 2 weeks after resolution of bleeding	Hold	5 mg daily	5 mg twice daily 

For cycles 2, 3, and 4, if platelets improve to  $>100 \times 10^9$ /L, a dose increase to 10 mg twice daily may be considered.

### 8.5 Re-screening Eligibility for Cycles 2- 4

Patients will be screened for eligibility to continue onto each subsequent cycle of therapy. Patients with disease progression, new GVHD (except grade I acute GVHD), prolongation of the most recent cycle to more than 8 weeks (for any reason), or inadequate cell dose for further DLI will not receive further treatment on study. Rescreening will be an ongoing process. When patients meet the eligibility criteria outlined below, they may begin subsequent cycles.

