### **15.3 Sample Size**

This study is designed as a two-stage phase II trial to estimate OS. Since the goal is to estimate the OS at a long-term time-point (6 months), our design is a generalization of the Simon design. Rather than suspension of the trial for evaluation after stage 1, this design uses an optimal interim analysis for futility without suspension of accrual as proposed by Huang et al. The goal of this design minimizes the expected sample size under the assumed parameters. Our trial assumes that a 6-month OS of 25% is unacceptably low and a 6-month OS of 50% is a rate worthy of further study. Both the null and alternative hypotheses assume that the OS follow an exponential distribution. Given an overall one-sided type I error of 5%, 32 evaluable patients will provide 80% statistical power.

When 14 patients have been enrolled (stage 1), it is expected that the accrual will stop if the 6 month Kaplan-Meier estimate of OS is less than 30.0%. It is not required that the 14th patient be followed for 6 months prior to making a decision of whether to continue the trial. Once the 14th patient has been enrolled, the statistician can calculate survival to determine if it falls below the cut-point. If the trial reaches the end of stage II after 32 evaluable patients, significant clinical activity would require at least a 6 month Kaplan-Meier estimate of OS of 39.2%. The probability of stopping at the interim analysis under the null hypothesis is 63.5% and 10.9% under the alternative hypothesis. The R package 'Optinterim' with functions 'OptimDes' and 'SimDes' were used to create design parameters. Assuming that 5% of enrolled patients are not evaluable, we expect recruitment of 34 patients.

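### Section 15.1 makes evaluability depend on a first dose of both drugs, so a patient already given decitabine can be removed and replaced in the primary survival analysis if ruxolitinib is held and never started

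*Combined protocol and SAP*

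**What the plan says.** - **Evaluability.** Section 15.1: "Patients are considered evaluable if they receive the first dose of decitabine and ruxolitinib. All other patients will be replaced." The same section measures OS from day 1 of cycle 1.
- **Replacement.** Section 7.2 covers registered patients who turn out unable to begin study treatment, described as starting with ruxolitinib and decitabine: "The patient will be replaced to complete enrollment."
- **Start of ruxolitinib.** Section 8.1 gives "5 mg twice daily orally beginning Day 1 and through Cycle 1", attaches no platelet condition to the first dose, and refers to Section 8.4 for toxicity modification. Decitabine has no dose modifications.
- **Hold.** Table 5 is keyed to "Non-transfused platelets" and says to hold ruxolitinib below 10 x10^9/L. A separate column says to hold it for grade 3 or greater bleeding related to low platelets. Section 8.4 calls the adjustment recommended.
- **Eligibility.** Sections 5.1, 5.2 and 8.5 contain no platelet minimum.
- **Decision rule.** Section 15.3 assumes that "a 6-month OS of 25% is unacceptably low and a 6-month OS of 50% is a rate worthy of further study". "Given an overall one-sided type I error of 5%, 32 evaluable patients will provide 80% statistical power." At stage 1, "it is expected that the accrual will stop if the 6 month Kaplan-Meier estimate of OS is less than 30.0" per cent; at the end, "significant clinical activity would require at least a 6 month Kaplan-Meier estimate of OS of 39.2" per cent.
- **A second statement.** Section 8.8 says that patients who receive at least one cycle are evaluable under Section 15.

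**The concern.** Take two patients who enter with very low platelets, both given decitabine on Day 1 with ruxolitinib held under Table 5. One dies in week 3 with ruxolitinib still held; 15.1 makes that patient non-evaluable and brings in a replacement. The other lives until the hold is lifted, takes one tablet and is counted, with survival time credited back to day 1 of cycle 1. The only difference between them is how long they lived, which is the outcome being measured.

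Membership of the primary analysis set is thus settled after treatment has begun and can depend on survival. In a single-arm trial judged against a fixed 25% benchmark there is no control arm in which the same selection would cancel. Inclusion could also vary by site, according to whether Table 5 is applied to the first dose. At the interim, a living patient on hold would have undetermined status.

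**Working it through.** **1. Does the text allow the exclusion?** Set side by side: no platelet minimum at entry (5.1, 5.2); a hold at low counts with no exemption for Day 1 (Table 5); decitabine given regardless (8.1); both first doses required and all others replaced (15.1). Low entry counts are foreseen, since Section 12.2 records prolonged grade 4 thrombocytopenia only if the pre-treatment count was above 100 x10^9/L. The sequence is possible on the text as written.

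**2. Reproduce the plan's figures.**
- Enrolment: 32 / (1 - 0.05) = 33.7, so 34. This matches 15.3.
- Final rule with complete 6-month follow-up: 0.392 x 32 = 12.5, so at least 13 of 32 alive. P(X >= 13 | 32, 0.25) = 3.8% and P(X >= 13 | 32, 0.50) = 89.2%, ignoring the interim.
- Two-stage rule by simulation (exponential survival, Kaplan-Meier look at the 14th entry without suspending accrual, cuts 30.0% and 39.2%, accrual 1.0 to 1.42 patients per month): power 79.7-82.7% (stated 80%); interim stopping 60-66% under the null (stated 63.5%) and 11-14% under the alternative (stated 10.9%). The attained type I error is about 3%, inside the 5% limit.

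**3. Effect of removal.** Inputs that are assumptions, not in the documents: a share f of treated patients never receives ruxolitinib, has 6-month OS q, and is fully replaced; true OS over all treated patients is 25%. Then

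OS among those counted = (0.25 - f x q) / (1 - f).

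Example: f = 0.10, q = 0.05 gives (0.25 - 0.005) / 0.90 = 27.2%.

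The two-stage rule is then simulated at that OS, treating counted patients as one exponential population and applying the interim to counted patients.

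| f | Treated patients needed, 32/(1-f) | OS among counted (q = 15% to 5%) | False-positive rate |
|---|---|---|---|
| 0 | 32 | 25.0% | about 3% |
| 5% | 34 | 25.5-26.1% | 3.5-4.2% |
| 10% | 36 | 26.1-27.2% | 4.3-5.6% |
| 20% | 40 | 27.5-30.0% | 6.1-11.1% |

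Ranges cover both the values of q and differences between simulation runs.

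With a harsher assumption, q = 10% down to 0, the rates are 4.0-4.8% at f = 2/34, 4.5-6.6% at 10% and 8.3-14.2% at 20%. With q = 25% the formula returns 25% for any f, so there is no bias.

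**The case against.** The best defence is that 15.1 simply means the patient began treatment. The synopsis, Section 4 and Section 8.1 start both drugs together on Day 1, Section 7.2 describes beginning treatment the same way, and Table 5 is a recommended toxicity adjustment that nothing says governs the first dose. On that reading hardly anyone gets decitabine alone. This is a fair reading, but not one the text secures. Table 5 is keyed to absolute counts, its top column carries the starting dose, and its footnote confines only the increase to cycles 2-4. Nothing exempts Day 1.

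Further points, and what stands of each:

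- *With no deadline, a later dose restores evaluability.* True, and it limits the number lost. It also makes inclusion depend on surviving until that dose.
- *Section 8.8 counts anyone with one cycle.* It may cover patients who complete a cycle. It does not clearly cover death or withdrawal within cycle 1, and it refers back to Section 15.
- *Exclusion 5.2.13 lets the investigator keep out high-risk patients.* It is discretionary, so it may reduce the number but does not close the route.
- *The interim is triggered at 14 enrolled, not 14 evaluable, and 15.2 names no analysis population.* Correct: that the 30.0% cut would use the reduced set is an inference. The 32 at the final analysis are expressly evaluable patients.
- *The objective is the combination's efficacy, so requiring both drugs is a legitimate treated set.* It is a recognisable choice, but here it is applied after treatment starts and can depend on the outcome.
- *The effect is small at planned attrition.* This stands. The 5% allowance covers every reason for non-evaluability, and 20% removed would need 40 treated patients against about 34 planned.

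**Conclusion.** The evaluability rule permits a treated patient to be removed from the primary analysis in a way that depends on how long they live. That is a real defect in the definition and worth correcting. Its size is unknown. At the planned 5% non-evaluable share, the false-positive rate stays under the stated 5% in every scenario examined. It passes 5% at about 10% removed only if 6-month OS in those patients is around 5% or lower, and at 20% removed it does so throughout the ranges of q below the null that were tried. All of this rests on assumed f and q and on a true OS of 25%.

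A reader might infer that the plan does drop its most thrombocytopenic patients, that healthier ones replace them, and that reported OS will therefore be too high. The documents do not support that. They do not show that any patient will miss ruxolitinib entirely, how many enter below 10 x10^9/L, or that such patients survive less well. The exclusion is possible, not demonstrated, and the upward bias is conditional on worse survival among those removed.

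**What to change.** In Section 15.1, define the primary OS set, for both the interim and final estimates, as all patients who received any dose of decitabine or ruxolitinib, with survival counted from day 1 of cycle 1. In 15.1 and 7.2, limit replacement to patients who received neither drug. Align the evaluability wording in 8.8 with this. Report the number of replaced patients, with their survival where known.

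Sections 8.1 and 8.4 (Table 5) must be reconciled by the sponsor on whether Table 5 applies to the first ruxolitinib dose. No clinical rule is proposed here, and the change to the analysis set works whichever way that is settled.

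Cost: one sentence each in 15.1 and 7.2 and a wording change in 8.8. The target of 32, the 30.0% and 39.2% cuts and the study procedures stay as they are. The downside is that estimated OS may be slightly less favourable, because a few patients who never received ruxolitinib would be counted.
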